### **5.6.3.1 CNS Symptoms Temporally Associated with ARIA-E MRI Findings**

CNS symptoms temporally associated with ARIA-E are defined as onset or worsening of CNS symptom(s) that is/are temporally associated with ARIA-E MRI findings. CNS symptoms experienced by the participant that are new or worsened since the last MRI without ARIA-E are collected in a CNS Symptoms Request Form before the MRI takes place at a visit. To identify CNS symptoms temporally associated with ARIA-E MRI findings, the following definitions will be used:

**NEW CNS symptoms:** If there is any AE reported in the eCRF with “Reported on the MRI CNS symptoms request form” = Y that is [new since date of most recent MRI scan showing no ARIA-E findings] AND is [ongoing or ends between the date of most recent site visit prior to date of MRI scan showing new ARIA-E (MRI) and date of MRI scan showing ARIA-E resolution (MRI)] then ARIA-E should be classified as associated with CNS symptoms

OR

**WORSENERD CNS symptoms:** If there is any AE reported in the eCRF with “Reported on the MRI CNS symptom request form” = Y that is [started before the date of most recent MRI scan showing no ARIA-E findings ] AND is [ongoing or ends between the date of

most recent site visit prior to date of MRI scan showing new ARIA-E (MRI) and date of MRI scan showing ARIA-E resolution from MRI data ] AND [there is an increase in severity grading] then ARIA-E should be classified as associated with CNS symptoms.

The CNS symptoms temporally associated with ARIA-E MRI findings will be listed and summarized by treatment group and within this also by APOE ε4 genotype (number of alleles).

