1.2.3 Safety Overview

Nonclinical characterization of gantenerumab did not show any relevant safety findings. To date, ARIAs and ISRs are the identified risks for gantenerumab. No differences between active and placebo groups have been observed in laboratory parameters, physical and neurological examinations, vital signs, or electrocardiogram (ECG) parameters.

Amyloid-Related Imaging Abnormalities

In the double-blind phase of Study WN25203 (prodromal AD), ARIA events were time, dose, and *APOE* ϵ 4 allele status dependent. The incidence of ARIA-E was 0.8% in the placebo, 6.6% in the 105-mg gantenerumab, and 13.5% in the 225-mg gantenerumab groups. For ARIA-H, the incidence was 13.2% in the placebo, and 22.9% and 16.2% in the 105-mg and 225-mg gantenerumab treatment groups, respectively. The rates of new ARIA-E were highest between 3 and 6 months of treatment (3.8% and 7.5% in the 105-mg and 225-mg gantenerumab groups, respectively) and decreased substantially after

the first year of treatment (incidence of up to 2.3% in the 225-mg gantenerumab group in approximately 2 years). The median MRI Barkhof grand total score (BGTS) (Barkhof et al. 2013) of these findings was 3. Most ARIA events were asymptomatic and did not lead to clinically significant consequences. A total of 5 patients (1.8%) from the 105-mg gantenerumab arm and 6 patients (2.3%) from the 225-mg gantenerumab arm experienced symptoms related to ARIA findings; the most commonly reported symptom was headache (5 patients). Other symptoms reported with ARIA-E included visual disturbances (left eye diplopia and upper left quadrantanopia), focal seizure (dysarthria/aphasia that lasted for 10 minutes), anxiety, hyperreflexia, confusional state, disturbance in attention, cognitive disorder, malaise, and dizziness. Symptomatic ARIAs were of mild severity and were non-serious except for one serious adverse event of focal seizure.

Following the futility analysis for Study WN25203, treatment in the double-blind phase was discontinued in July 2017 (median double-blind treatment duration: 68 weeks) and consenting patients transitioned into OLE.

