- ^h Limited, symptom-directed physical examinations; changes from baseline abnormalities should be recorded in participant notes.
- ⁱ MRI must be performed at least 7 days before dosing and results must be available for review by site staff before dosing can proceed. MRI should be performed before or at least 3 days following a lumbar puncture.
- ^j Includes resting-state functional MRI and DTI outcome measures, where available.

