Appendix 6: Management Rules for Amyloid-Related Imaging Abnormalities (cont.)

ARIA-E = amyloid-related imaging abnormality–edema/effusion; ARIA-H=amyloid-related imaging abnormality–hemosiderin deposition; BGTS=Barkhof grand total score; LH=leptomeningeal hemosiderosis; MRI=magnetic resonance imaging; Q2W=every 2 weeks.

In exceptional cases of (1) an ARIA-E that is asymptomatic with BGTS <4 and considered stable over consecutive MRI images by the Sponsor and investigator; or (2) symptomatic ARIA-E for which the imaging evidence of ARIA-E has resolved but the CNS symptoms continue, study drug can be either reintroduced or uptitrated, as applicable, and 4-weekly MRI monitoring may no longer be necessary, as determined by the Sponsor and investigator.

Symptomatic ARIA-E is defined as onset or worsening of CNS symptom(s) that is/are temporally associated with ARIA-E MRI findings

A PK and a plasma biomarker sample will be obtained as soon as is practical (e.g., at an unscheduled visit) once the site becomes aware of the occurrence or worsening of ARIA-E or of the occurrence of ARIA-H meeting discontinuation criteria

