### **5.6.3 Magnetic Resonance Imaging Safety Findings**

ARIA-E and ARIA-H are identified risks associated with gantenerumab. Sites were asked to capture all ARIAs as AEs in the eCRF that met any of the following criteria:

- Symptomatic ARIA-E (i.e., accompanied by CNS symptoms), and/or

- ARIA findings that result in a change in study treatment (e.g., dosage modification, treatment interruption, or treatment discontinuation), and/or
- Findings that are otherwise clinically significant in the investigator’s judgment

Not all ARIA MRI findings qualify as AE. ARIA analyses will be mainly based on ARIA MRI findings. ARIA AEs will also be reported. Based on MRI data, the incidence, and severity (based on the Barkhof Grand Total Score [BGTS]) ARIA-E and the incidence of ARIA-H will be summarized by treatment group and within this also by APOE ε4 genotype (by number of alleles) and by dose level. Additionally, the timing of ARIA-E and the timing to meet the protocol-defined criteria for permanent discontinuation due to ARIA-H will be also summarized by descriptive statistics and eventually by Kaplan-Meier methods. Recurrence of ARIA-E will be summarized by treatment group and within this also by APOE ε4 genotype (by number of alleles). ARIA-E associated with CNS symptoms (see Section 5.6.3.1) and with serious CNS symptoms will be summarized by treatment group and within this also by APOE ε4 genotype. Temporal co-occurrence of ARIA-E and ARIA-H will be summarized by treatment group and within this also by APOE ε4 genotype (by number of alleles). Temporal co-occurrence is defined as an MRI scan showing new ARIA-H that occurs between ARIA-E onset and resolution (inclusive), irrespective of the brain region.

MRI findings other than ARIA will also be summarized.

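### The end-date condition in SAP 5.6.3.1 can omit CNS symptoms that resolved before the last site visit from the symptomatic ARIA-E tables

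*SAP*

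**What the plan says.** SAP 5.6.3.1 starts from a form completed before each MRI: "CNS symptoms experienced by the participant that are new or worsened since the last MRI without ARIA-E are collected in a CNS Symptoms Request Form". It then gives two routes to classing an ARIA-E finding as associated with CNS symptoms.

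- **New symptom:** the adverse event is flagged as reported on the form, its onset falls after the last clean scan, and it passes an end-date condition: "ongoing or ends between the date of most recent site visit prior to date of MRI scan showing new ARIA-E". The far end of that interval is the resolution scan.
- **Worsened symptom:** the event began before the last clean scan, meets the same end-date condition, and has increased in severity grade.

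In both routes the conditions are joined by AND. The result feeds SAP 5.6.3: "ARIA-E associated with CNS symptoms (see Section 5.6.3.1) and with serious CNS symptoms will be summarized by treatment group". These summaries are also split by APOE ε4 genotype inside each arm.

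Protocol 5.1.2 and Appendix 6 define symptomatic ARIA-E as CNS symptoms whose onset or worsening is temporally associated with the MRI finding. Neither sets a condition on when the symptom ends.

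**The concern.** Collection and classification cover different periods. The form reaches back to the last scan without ARIA-E. The rule then keeps a symptom only if it was still present at, or ended after, the last site visit before the scan. A symptom that began and resolved between the clean scan and that visit is collected, flagged and then left out.

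ARIA is an identified risk of the drug, and the symptomatic and serious-symptomatic tables describe its clinical consequences. Brief events belong to that picture. The one serious symptomatic ARIA in the double-blind phase of WN25203 was a focal seizure with a speech disturbance lasting 10 minutes (Protocol 1.2.3). In the open-label extensions, four of the seven serious terms named there were seizure or epilepsy. ARIA-E also arises mainly on active drug (0.8% on placebo against 13.5% on 225 mg in WN25203), so missed classifications would fall mainly in that arm.

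**Working it through.** The plan states no figure for this rule, so there is none to reproduce. The check applies the rule as written to constructed dates and then measures the window.

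**1. The rule on a one-day seizure.** An event counts if it is flagged, its onset is after the clean scan, and it is either ongoing or satisfies: last site visit before the scan ≤ end date ≤ resolution scan. The clean scan is on day 413. Routine visits are two-weekly, on day 7 × week + 1.

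| Case | Seizure | Last site visit before scan date | Scan showing ARIA-E | Counted? |
|---|---|---|---|---|
| A | 470 | 463 | 475 | Yes |
| B | 470 | 472 (unscheduled) | 475 | No |
| C | 470 | 470 | 475 | Only if the boundary is inclusive |
| D | 470 | 463 (a visit on 472 shares the scan date) | 472 | Yes |
| E | 440 | 519 | 526 (scheduled) | No |

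A and B have the same event, the same scan and the same 5-day gap. Only the intervening visit differs. The protocol provides for both unscheduled visits (4.6.8) and unscheduled MRI for CNS events (4.5.9).

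**2. Look-back before a scheduled scan, all visits on site.** Protocol Appendix 1 states: "MRI must be performed at least 7 days before dosing and results must be available for review by site staff before dosing can proceed". Assume the scan falls between the preceding dosing visit and the one it precedes.

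- Two-weekly dosing: at most 14 − 7 = 7 days. Against scheduled scan intervals this is 7/84 = 8.3% (Weeks 36–48, 48–60, 104–116), 7/112 = 6.25% (Weeks 60–76) and 7/196 = 3.6% (Weeks 76–104).
- Four-weekly titration: at most 28 − 7 = 21 days. The recommendation to scan at least 10 days after the third dose of a step gives a lower end of 10. The share is 10/84 to 21/84, or 12% to 25%.

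**3. Look-back if home visits are used and do not count.** Appendix 1 marks Weeks 16, 20, 28, 32, 42–50, 54–74 and 78–102 as suitable for home administration. With scans one week before dosing, and attendance for a scan not itself counted as a site visit:

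| Scan for | Last site visit | Look-back |
|---|---|---|
| Week 24 | Week 12 | 23 − 12 = 11 weeks, 77 days |
| Week 36 | Week 24 | 35 − 24 = 11 weeks, 77 days |
| Week 48 | Week 41 | 47 − 41 = 6 weeks, 42 days |
| Week 60 | Week 52 | 59 − 52 = 7 weeks, 49 days |
| Week 76 | Week 52 | 75 − 52 = 23 weeks, 161 days |

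All exceed 28 days. Under this reading case E changes to counted, because the last site visit becomes Week 52 (7 × 52 + 1 = day 365), before the seizure on day 440.

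**4. Size of the rows (illustration only).** Assume the predicted ARIA-E rate of about 26% (Protocol 1.3.2) and the open-label extension symptom rates in Protocol 1.2.3 carry over. Then 0.26 × 508 ≈ 132 active-arm cases. Symptomatic: (11 + 18)/(47 + 71) = 29/118, giving about 32. Serious: (3 + 4)/118 = 7/118, giving about 8. One lost serious case would change that row by about one eighth.

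**5. Upper limit and undefined terms.** The rule does not say whether *ongoing* covers an event that ends after the resolution scan. Protocol 5.1.2 and Appendix 6 provide for "symptomatic ARIA-E for which the imaging evidence of ARIA-E has resolved but the CNS symptoms continue". A resolution scan may also be missing: follow-up after treatment withdrawal excludes MRI (Protocol 4.7.1), and four-weekly MRI may stop for stable ARIA-E (5.1.2). *Site visit* is undefined, and inclusivity is unstated here although SAP 5.6.3 states it for co-occurrence of ARIA-E and ARIA-H.

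**The case against.** **Some proximity limit is legitimate.** Temporal association implies one, and dropping the end-date test lets a symptom count from as far back as the last clean scan, up to 196 days. Headache (7.0%) and dizziness (5.7%) were common across arms in WN28745 (Protocol 1.2.2.3), so unrelated transient symptoms would enter. This stands, and it is why both tables are needed. It does not rescue the present limit, which depends on when a visit happened to occur rather than on the time from symptom to scan.

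**The events are not lost to the report.** Protocol 5.3.5.1 requires symptomatic ARIA-E to be reported as an adverse event and accompanying symptoms to be recorded separately, and SAP 5.6.3 also reports ARIA adverse events. This stands too. But the SAP bases its ARIA analyses mainly on MRI findings, and a general event table does not link a symptom to an ARIA-E finding.

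**Stronger readings that the documents do not support.** A reader might infer that a seizure prompting an MRI is always dropped. It is dropped only when a site visit falls after the seizure ends and before the scan date; cases A and D are kept. A reader might infer that omitted cases are reported as asymptomatic, but the SAP uses no such label. Nor can anyone say that the 10-minute seizure in WN25203 would have been dropped, because its visit and scan dates are not given. Finally, symptoms outlasting the imaging finding are listed among exceptional cases, so the upper limit needs clarification rather than being a routine source of loss.

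**Conclusion.** The concern holds as a classification weakness in a descriptive safety table. Read as written, SAP 5.6.3.1 omits a flagged symptom that began after the last ARIA-E-free scan and resolved before the last site visit preceding the ARIA-E scan, and the finding then leaves the symptomatic and serious-symptomatic tables unless another symptom qualifies. The likely direction is undercounting, mainly on active drug. No hypothesis test is affected.

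The size is not known. The look-back runs from at most 7 days (two-weekly dosing, every visit on site, nominal dates) to more than 28 days (home visits used and not counted as site visits). A reader might turn the 7-day window into a proportion of symptomatic cases lost. That is not supported: the window shares describe the schedule, they rest on an undefined term, and the documents give no data on symptom timing or duration. The row sizes in the working are an illustration that depends on earlier-study rates carrying over.

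**What to change.** Add a tabulation of ARIA-E associated with any form-flagged CNS adverse event that starts or worsens after the most recent MRI without ARIA-E and on or before the resolution scan, whatever its end date. Where there is no resolution scan, use the last available scan or the data cut-off. Show it beside the current narrower definition, by arm and APOE ε4 genotype, for all and for serious CNS symptoms.

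In the same section, state whether *site visit* includes unscheduled and home visits, that the boundaries are inclusive, and that *ongoing* covers events ending after the resolution scan.

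The cost is SAP wording and one further derivation. The form flag and event dates are already collected. The documents do not say whether a date of worsening is recorded; if it is not, the form flag together with the increase in severity grade has to stand in for it. The downside is that some unrelated transient symptoms will be counted under the broader definition, in either arm.

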- In exceptional cases of 1) an ARIA-E that is asymptomatic with BGTS < 4 and that is considered stable over consecutive MRI images by the Sponsor and investigator; or 2) symptomatic ARIA-E for which the imaging evidence of ARIA-E has resolved but

the CNS symptoms continue, the study drug can either be reintroduced or uptitrated, as applicable, and 4-weekly MRI monitoring may no longer be necessary, as determined by the Sponsor and investigator.

- Symptomatic ARIA-E is defined as onset or worsening of CNS symptom(s) that is/are temporally associated with ARIA-E MRI findings.
- Any recurrence of ARIA-E: Treat using the same procedures as for the first event (based on symptoms and BGTS).
- Participants who develop > 15 ARIA-H cumulatively will be discontinued from study drug (the cumulative number should not include any disseminated leptomeningeal hemosiderosis, i.e., up to 3 focal leptomeningeal hemosiderosis *either on the same scan or cumulatively*; a focal leptomeningeal hemosiderosis is counted as an ARIA-H).
- In cases where both ARIA-E and ARIA-H occur, the most conservative approach should be followed.
- A PK sample and a plasma biomarker sample will be obtained as soon as is practical (e.g., at an unscheduled visit) once the site becomes aware of the occurrence or worsening of ARIA-E or ARIA-H that meet the discontinuation criteria.
- The investigators may choose to perform additional MRI monitoring for ARIA at any time.
- MRI monitoring of ARIA findings should be conducted at approximately 4-week intervals.
- Any other new significant findings will be reviewed by the medical monitor and appropriate dose action will be taken.

The iDMC reviews the incidence of ARIA in an unblinded manner and may recommend adjustment of dosing regimen and/or ARIA management for the overall study population or for a specific *APOE* ε4 genotype.

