5.3.5.5 Persistent or Recurrent Adverse Events

A persistent adverse event is one that extends continuously, without resolution, between participant evaluation timepoints. Such events should only be recorded once on the Adverse Event eCRF. The initial severity (intensity or grade) of the event will be recorded at the time the event is first reported. If a persistent adverse event becomes more severe, the most extreme severity should also be recorded on the Adverse Event eCRF. If the event becomes serious, it should be reported to the Sponsor immediately (i.e., no more than 24 hours after learning that the event became serious; see Section 5.4.2 for reporting instructions). The Adverse Event eCRF should be updated by changing the event from “non-serious” to “serious,” providing the date that the event became serious, and completing all data fields related to serious adverse events.

A recurrent adverse event is one that resolves between participant evaluation timepoints and subsequently recurs. Each recurrence of an adverse event should be recorded as a separate event on the Adverse Event eCRF.

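### The worsened-symptom rule in SAP 5.6.3.1 does not date the severity increase, so a CNS symptom that worsened outside the ARIA-E episode can make that ARIA-E count as symptomatic

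*SAP*

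**What the plan says.** Protocol 5.1.2 gives the definition to be implemented: "Symptomatic ARIA-E is defined as onset or worsening of CNS symptom(s) that is/are temporally associated with ARIA-E MRI findings". SAP 5.6.3.1 opens with the same idea and turns it into two alternative rules for the analysis.

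- **New symptoms.** The adverse event must be "new since date of most recent MRI scan showing no ARIA-E findings", so the triggering event, the onset, has a lower date bound.
- **Worsened symptoms.** The adverse event must have "started before the date of most recent MRI scan showing no ARIA-E findings". It must be ongoing, or end between the last site visit before the new ARIA-E scan and the "date of MRI scan showing ARIA-E resolution from MRI data". Finally, "AND [there is an increase in severity grading] then ARIA-E should be classified as associated with CNS symptoms".

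Both rules also need a yes in the adverse event field "Reported on the MRI CNS symptom request form" (the new-symptom rule words it almost identically). The SAP describes the form as follows: "CNS symptoms experienced by the participant that are new or worsened since the last MRI without ARIA-E are collected in a CNS Symptoms Request Form". It is completed before the MRI takes place.

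On recording severity, Protocol 5.3.5.5 has sites enter the initial grade of a persistent event and adds: "If a persistent adverse event becomes more severe, the most extreme severity should also be recorded on the Adverse Event eCRF". The same section asks for the date on which an event became serious. It mentions no date for a rise in severity.

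**The concern.** In the worsened-symptom rule the event of interest is the worsening. The rule dates when the adverse event began and whether or when it ended, but not when it got worse. A persistent event carries an initial and a most extreme grade, so any rise during its life meets the condition.

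The form flag does not supply the missing date. It is a property of the adverse event, not of a particular scan. Forms are completed before the scan result is known, so they also precede scans that turn out clean, and a yes may come from a form for some other scan.

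ARIA-E is an identified risk of the drug. SAP 5.6.3 plans summaries of ARIA-E with CNS symptoms, and with serious CNS symptoms, by arm and APOE ε4 genotype. ARIA-E is expected mainly in the active arm, so false symptomatic cases would fall mainly there.

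**Working it through.** **1. What each condition dates**

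| Condition | New-symptom rule | Worsened-symptom rule |
|---|---|---|
| Onset of the adverse event | After the last clean MRI | Before the last clean MRI |
| Ongoing or end status | Relative to the ARIA-E window | Relative to the ARIA-E window |
| Form flag | Yes on the event, no scan named | Yes on the event, no scan named |
| Triggering event | Onset: dated | Severity increase: not dated |

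Nearby, SAP 5.6.3 bounds the co-occurrence of ARIA-E and ARIA-H from ARIA-E onset to resolution, inclusive. The undated condition is out of line with the SAP's own practice.

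**2. Applying the rule to a timeline**

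Scheduled MRIs fall at Weeks 12, 24, 36, 48, 60, 76, 104 and 116 (Protocol Appendix 1). Assumed case: last clean MRI Week 24, last site visit before the ARIA-E scan Week 32, ARIA-E seen Week 36, resolution scan Week 48. A CNS symptom starts at Week 14 and is reported as new on the form before the Week 24 scan, which sets the flag. Only the week of the severity increase is varied.

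The rule was applied in three ways: as written; with the flag restricted to the forms for the ARIA-E scan or the resolution scan; and with the increase required after Week 24 and by Week 48.

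| Symptom ongoing, increase at week | As written | Flag tied to episode | Increase dated |
|---|---|---|---|
| 16, 20, 23 (before the clean scan) | symptomatic | no | no |
| 26, 30, 34, 40, 46 (within the episode) | symptomatic | symptomatic | symptomatic |
| 52, 70, 100 (after resolution) | symptomatic | no | no |

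As written, 11 of 11 dates qualify. Either correction leaves 5 of 11. If the symptom ends at Week 40, inside the window, increases at Weeks 16, 20, 23, 26, 34 and 38 all qualify as written (6 of 6). Either correction leaves 3 of 6 (Weeks 26, 34 and 38). In that second case no increase after resolution is possible.

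For a flagged event that meets the start and end conditions, the result as written does not depend on when severity rose. These counts show how the rule behaves. They are not estimates of how often misclassification would happen.

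**3. Scale**

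- Expected ARIA-E rate: about 26% (Protocol 1.3.2). Planned active arm: 508 (Protocol 3.1.1).
- Expected ARIA-E cases: 0.26 × 508 = 132.1.
- Effect of one false case on the symptomatic share of ARIA-E cases: 100 / 132.1 = 0.76 percentage points.
- If the denominator is instead the whole active arm: 100 / 508 = 0.20 points.

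For context, Protocol 1.2.3 reports CNS adverse events in 11 of 47 and 18 of 71 patients with ARIA-E in the two extension studies: (11 + 18) / (47 + 71) = 29 / 118 = 24.6%.

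**The case against.** The strongest reply is that the form already supplies the date. It collects symptoms that are new or worse since the last MRI without ARIA-E. If the flag means the form for the scan being classified, a symptom that worsened before the clean scan and then stayed stable would not be on it, nor would a worsening after resolution. The table confirms that both kinds of case drop out on that reading. This shows that a lower bound was intended. It does not close the gap, because the rule asks only whether the adverse event carries a yes and does not say from which scan's form.

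Several other points stand:

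- The undated increase is not enough alone. The event must carry the flag, start before the last clean scan, rise in grade, and be ongoing or end in the window. A symptom that resolves and returns is a separate event under Protocol 5.3.5.5, which narrows the pool.
- The eCRF, the form, and Data Analysis Plan Modules 2 and 3 are not in the documents and may hold a date or a scan link. A reader might infer that severity increases are undated in the database. The documents only fail to mention such a date.
- The summaries are descriptive, the symptoms will be listed, and ARIA adverse events recorded by sites will also be reported, which gives a cross-check. This error would overstate a risk, not hide one.

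**Conclusion.** The point holds as a gap in a stated rule: followed literally, the rule can classify an ARIA-E as symptomatic on a worsening that lies outside the episode, contrary to the definition in Protocol 5.1.2 and in SAP 5.6.3.1 itself. It rests on reading the form flag as written, at the level of the adverse event. The term ongoing could mean ongoing in the window or at data cut-off; the gap exists on either reading.

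Three stronger readings are not supported. First, the rule does not make every pre-existing symptom that worsened count, because the other conditions must also hold. Second, no percentage can be put on the overstatement, because the documents do not say how often pre-existing CNS events with a grade increase occur or how the flag was set. The 0.76 points per case is a scale only and rests on the predicted 26% rate. Third, no efficacy test or type I error is affected; the effect is confined to the descriptive symptomatic and serious-symptomatic ARIA-E summaries.

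The change is worth making, because these summaries describe an identified risk of the drug.

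**What to change.** Before unblinding, first confirm what is collected: a date for each severity increase on the adverse event record, or scan-level entries on the request form that show which symptoms were reported as worsened.

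If increases are dated, replace the last condition of the worsened-symptom rule with: and the rise in severity grade took place after the last scan without ARIA-E and no later than the scan on which the ARIA-E is shown to have resolved.

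If they are not dated, require instead that the event was reported as worsened on the request form completed for that ARIA-E scan, or for a follow-up scan up to resolution. In the timeline above the two versions give the same classification.

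The cost is one SAP sentence and one condition in one derivation, provided one of these data items exists. If neither does, the SAP should say so, and the listing should mark cases that qualify only through the worsened-symptom rule. The downside is that the reported count of symptomatic ARIA-E may fall slightly, which is why the change should precede unblinding. It concerns the analysis classification only and leaves the protocol's ARIA management rules untouched.
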